## Section 1: Administrative Information

### **1) Title and trial registration**

- a. Changing Health Through Food Support for Diabetes (CHEFS-DM)
- b. Trial registration number: NCT04959487

### **2) Protocol/SAP version number with dates**

- a. Version 2 –02/05/2025
- b. Version 1 – 07/08/2021

## Section 2: Introduction

### **1) Background and rationale**

Type 2 diabetes mellitus (T2DM) affects 29.1 million persons in the United States (US), disproportionately impacting low-income communities. Forty million people in the US are also food insecure. Food insecurity – defined as limited or uncertain access to safe, nutritious food – is strongly associated with T2DM acquisition, and among people with T2DM, poor glycemic control. In 2017, 49 million Americans were food-insecure.

Food insecurity contributes to increased T2DM-related morbidity and mortality through nutritional (poor diet quality, obesity), mental health (stress, depression), and behavioral pathways (non-adherence, missed clinic visits). Food-insecure households often cope with inadequate food budgets by purchasing cheap, energy-dense foods, which are typically suboptimal for glycemic control. They often also live in neighborhoods with poor access to healthy foods (ex: fruits & vegetables). Together, these factors contribute to poor diet quality among food-insecure individuals, leading to worse outcomes for T2DM and other chronic illnesses. Existing nutrition safety-net resources are inadequate to address the health effects of food insecurity. Half of all CalFresh enrollees (California's "Food Stamps") continue to be food insecure, and 40% of food-insecure households receive no government aid at all. While 13% of Americans rely on community food programs, these programs seldom provide medically tailored diets. Policy makers increasingly recognize the premise that "Food is Medicine" (FIM), i.e., medically tailored food for chronically ill, food-insecure people, can play a critical role in achieving optimal health outcomes. As the evidence mounts that FIM may also save significant healthcare dollars, a growing number of programs seek to incorporate medically tailored food support into the healthcare system. Yet the evidence for the efficacy of FIM programs is nascent and significant gaps remain. There is an urgent need to develop, implement, and evaluate novel strategies to reach food-insecure individuals with T2DM to improve diabetes outcomes and reduce disparities.

Partnering with Project Open Hand (POH), a non-profit organization, that provides food support to San Francisco's and Oakland's most vulnerable residents with chronic illness, a pragmatic randomized controlled trial (RCT) of Changing Health through Food Support for Diabetes (CHEFS-DM) will be conducted. The study consists in a 6-month intervention providing supplemental food support meeting ~75% of daily energy requirements via a DM-tailored diet, and DM-focused nutritional education provided by POH registered dieticians (two sessions of individual counseling and four session of in-group diabetes-tailored nutrition education sessions). This RCT follows a pilot study in which the intervention was feasible, acceptable, and associated

with improvements in food security, diet quality, health behaviors, mental health, and trends towards improvements in acute care use, and clinical indicators.

## 2) Objectives

**Aim 1:** To determine the impact of CHEFS-DM on glycemic control and other cardiometabolic outcomes. The hypothesis is that CHEFS-DM will improve hemoglobin A1c (primary outcome), dyslipidemia, and health-related quality of life (HRQoL); blood pressure (BP) and acute care utilization; and improve diabetes medication adherence (secondary outcomes). Participants will be randomized to intervention versus control.. Data collection will include surveys, anthropometry, 24-hour dietary recalls, BP measures, medical record review, and blood draws. Characteristics of those most likely to benefit from CHEFS-DM will be described (e.g., poor T2DM control, gender).

**Aim 2:** To determine the impact of CHEFS-DM on intermediate outcomes that may mediate any impact of CHEFS-DM on T2DM health. Using our novel conceptual model, the hypothesis is that that CHEFS-DM will improve food insecurity (proximal intermediate outcome) which in turn will lead to improvements in nutritional (e.g., improved diet, body mass index), mental health (e.g., less diabetes distress, depression), and behavioral (e.g. improved medication adherence, diabetes self-management, and clinic attendance) paths (distal intermediate outcomes). Together these will improve T2DM control, cardiometabolic health, and HRQoL. Identifying the predominant causal paths will enable to further tailor the program to enhance impact during future implementation.

**Aim 3.** To determine the cost-effectiveness and sustainability of CHEFS-DM and obtain information to inform scale-up. a) The cost per quality-adjusted life year gained will be calculated; b) Whether any improvements in the intervention arm were sustained over 12 months of follow-up will be assessed; and c) A process evaluation will be performed, collecting qualitative and quantitative data with study participants and staff to determine what worked and did not work to guide future intervention scale-up efforts. The hypothesis is that the intervention may be cost-effective and possibly cost saving, and that health benefits will be sustained at 12 months.

## Section 3: Study Methods

### **1) Trial design**

A pragmatic RCT will be conducted to test the efficacy of CHEFS-DM, a six-month multicomponent food and nutrition intervention among low-income adults with T2DM, on diabetes health. Participants will be randomized 1:1 to the intervention, using a parallel design.

### **2) Intervention description**

Diabetes-tailored food support. The intervention group will receive six months of supplemental food support meeting on average 75% of their daily energy requirements in the form of a T2DM-tailored diet. POH staff will administer the intervention. Food support will consist of a mix of meals tailored for T2DM, and T2DM-healthy groceries, consistent with the American Diabetes Association (ADA) guidelines. Meals will be tailored to many common food preferences of the clients (e.g., vegetarian, pescatarian, no fish, low salt). Meals may be picked up at one of two fixed POH locations, at a POH mobile site (i.e., van that provides POH resources to neighborhoods without easy access to their locations with 3 locations in San Francisco and 1 location in Alameda County), or home-delivered for non-mobile individuals. POH will offer the option of food delivery to all participants during the coronavirus pandemic as needed to comply with changing COVID guidelines and as requested by participants because of the coronavirus pandemic. Mobile site hours may be limited due to the COVID pandemic.

Nutritional counseling and education. A registered dietitian from POH will meet with intervention participants individually two times (at baseline and month 5-6) for a 1-hour nutritional counseling support session. In addition, a registered dietitian from POH will conduct group-based nutrition education over four 1-hour-long sessions. The group-based session nutrition education will be consistent with published diabetes self-management education principles utilizing strategies shown effective in lower-income, lower-literacy populations. Nutrition education topics will include how to utilize and prepare POH food, understanding the role of diet and nutrition in T2DM health and management, strategies to shop for and prepare diabetes-healthy meals, reading nutrition labels, support and self- efficacy around maintaining a diabetes- healthy diet, reducing sedentary activity, and increasing physical activity including

aerobic exercise and strength training. POH will implement use of technology such as Zoom to conduct group class sessions as needed during the COVID-19 pandemic to be compliant with UCSF guidelines. Class sessions will be held in person, as originally planned, when it is safe and acceptable to do so, and remote options will continue to be available after the COVID-19 pandemic to improve accessibility.

Control condition. Control participants will receive the standard of care as offered by clinical partners to all T2DM participants, including referral to nutritional counseling, T2DM support groups, and participation to local diabetes self-management programs. Control participants are also often provided referral information for locally available food support services in the region that provide diabetes-appropriate foods. After 6-months, the control arm will have the opportunity to receive diabetes-tailored food support from POH along with nutritional counseling, regardless of whether they meet regular POH eligibility criteria. The services that the control group will receive after the six-month period will be similar to what the intervention group receives during the intensive CHEFS-DM intervention - 6-months of food sufficient to meet 67% of their daily requirements, video recordings of the 4 CHEFS- DM intervention nutrition education classes and access to a POH RD at their request.

Given that POH could not easily absorb a large number of additional new clients in a relatively short time frame, the wait time is also in line with programmatic considerations.

## 5) Data collection

Follow-up will be broken up into two phases. From baseline to six months, the CHEFS-DM intervention will be implemented, and researchers will follow both intervention and control arm participants (n=281 (actual)). After the end of the six-month follow-up, the intervention arm will transition to receiving standard POH services (comprising 33% to 67% of daily energy requirements depending on health status), and will be followed for an additional six months, to assess the extent to which any health benefits are sustained at 12 months (n=156). Hence, control arm will be followed for 6 months and participate in two assessments, and the intervention arm will be followed for 12 months and participate in three assessments.

At baseline and 6 months for all participants and at 12 months for intervention arm, the following data will be collected:

a) Structured interviews (baseline, 6 and 12 months). Trained UCSF research assistants (RAs), including Spanish/English bilingual RAs, will administer the structured interview either in person or over the phone and/or zoom, depending on public health protocols and acceptability of in-person visits to participants due to COVID-19. When visits are conducted in-person, interviews will take place in private offices at POH, in a private room at a partner clinic (if available), in a private location at a community space (e.g. library, community center), or at a private location of the participants choosing (e. g. home visit).

The content of the interviews will cover:

- Socio-demographic information.
- Food insecurity and diet quality
- Physical activity
- Mental health (e.g., depressive symptoms, diabetes distress and social support, self- efficacy for following T2DM recommendations).
- Adherence to T2DM medications.
- Health care utilization (e.g., missed clinic visits, acute care use (hospitalizations and emergency department visits)).
- Health-related quality of life.
- Medication inventory (for cardiometabolic conditions only).
- Diabetes co-morbidities (e.g. nephropathy, retinopathy).
- Economic information (e.g. economic impacts of COVID-19, household expenditures on food).
- In addition, at 6-month follow-up, the structured interview will also include questions to assess participant costs related to the intervention (e.g. transportation), food utilization (e.g. sharing, waste), barriers to intervention use, and program satisfaction among intervention participants, and use of free food resources (not including POH) among control and intervention participants.

b) Anthropometric assessments (baseline and 6 months). Anthropometry will be assessed by trained UCSF RAs at the same time as the structured interview, except when interviews are conducted by phone due to COVID. During COVID, UCSF staff may schedule anthropometric assessments separately from structured interviews to reduce exposure between staff and participants and will follow COVID safety guidelines for research (e.g. using personal protective equipment). UCSF RAs trained by clinicians in anthropometry will obtain three repeated measurements of weight (kg), height (cm), and waist and hip

- circumferences (cm). Tanita WB-800H portable digital scales will be used to measure the weight, SECA-213 stadiometer will be used to measure the height. For wheelchair-bound individuals RA will conduct anthropometry at a clinic with a wheelchair-accessible scale and stadiometer. At baseline and six months, all participants will undergo anthropometry
- c) Blood pressure assessments (baseline and 6 months). Blood pressure (BP) will be assessed by trained UCSF RAs at the same time as the anthropometry. BP will be measured using the Omron HEM 907XL IntelliSense Professional Digital Blood Pressure Monitor. Three blood pressure measurements will be taken after three to five minutes of inactivity and averaged to obtain a more accurate measure. At baseline and six months, all participants will undergo blood pressure measurements; at twelve months, blood pressure will be assessed in the intervention arm only.
- d) Blood draws (baseline, 6, and 12 months): Participants will undergo a blood draw (testing a lipid panel, and HemoglobinA1c) at one of 28 Quest Diagnostics labs in San Francisco or Alameda counties Phlebotomy will be performed using universal precautions. Date and time of phlebotomy, and specimen number will be recorded in a participant log. Specimens will be aliquoted and stored at -70°C using standard universal precautions. Data will be received from Quest Diagnostics in the form of a spreadsheet which can be easily merged with other study data by participant ID or will be accessed by UCSF staff using the secure Quest Diagnostics HIPPA-compliant online portal. At baseline and six months, all participants will undergo the blood draw; at twelve months, the blood draw will be implemented in the intervention arm only.
- e) 24-hour Dietary Recall (baseline and 6 months). Dietary intake will be assessed via 24-hour dietary recalls by UCSF RA trained by registered dietitians using the National Cancer Institute's Automated Self- Administered 24-hour Dietary Recall (ASA24). Participants will complete two unannounced recalls (one weekday and one weekend day) during a one-week period. In total, participants will complete four recalls: 2 at baseline and 2 at 6-month follow- up. RA's will inform the participant of which week the calls will be attempted. Previous work has indicated that lower income or older adults may need additional assistance with completing the ASA24, therefore the questions will be administered over the phone or in person (if COVID permits), using strategies to ensure the collection of dietary data is accurate and does not burden the participant. The 24-hour dietary recall will be conducted at baseline and six-month follow up.
- f) Medical record review (baseline, 6, and 12 months). Medical records will be used

during recruitment to confirm T2DM diagnosis, to confirm participant HbA1c, preferentially greater than or equal to 6.5%, and to determine whether a patient has controlled or uncontrolled T2DM using latest HbA1C test result. Medical record review is also being used to collect follow-up HbA1c data if completing a blood draw is not possible during follow-up, if medical record A1c is available within the assessment time frame, and with the consent of the participant.

g) Qualitative interviews. In-depth, semi-structured interviews of 60-90 minutes will be conducted by UCSF RAs with up to 40 participants, including both completers and non-completers of the intervention. Most of these interviews will occur after the 6-month intensive phase of the intervention, with approximately 10 interviews at the end of 12 months. UCSF RAs will also interview up to 20 key informants including POH staff, study personnel, and clinicians from safety net clinics. Interviews will focus on mechanisms underlying program impacts, including possible nutritional, behavioral and mental health pathways. Other topics that will be asked during the interview are related to factors affecting program adherence and satisfaction, strengths and limitations of the CHEFS-DM intervention, barriers and facilitators to program participation, and suggestions for scale-up. The 12-month interviews will provide insight on experiences with transitioning to POH regular programming, and issues related to sustainability of any perceived impacts. Interviews will be conducted in English or Spanish by bilingual UCSF RAs, audio-recorded, and transcribed in the original language. The interviews will be conducted either over the phone and/or zoom or in-person, if able to do so per COVID-19 guidelines and based on the acceptability of meeting in-person among participants.

h) Administrative records from POH. POH will provide the following information:

- o Intervention costs incurred by POH. POH will provide administrative records of program expenditures to track all intervention costs, excluding research costs. These costs come from goods (the food and packaging), personnel, and fixed infrastructure and overhead.
- o Records of pick-up and/or receipt of delivered food. POH will provide administrative records of weekly pick-up and/or delivered food for each participant.

#### 4) Randomization

281 participants were randomized 1:1 to the intervention and control arms,

stratified by county (San Francisco vs. Alameda County) and poor diabetes control (A1c < 9%, vs.  $\geq$  9%). Details of the randomization and stratification method is stored securely in REDCap. Randomization based on a computer-generated assignment will occur after the participant has provided informed consent and completed baseline assessments.

## 5) Sample size

The sample size was determined based on power calculations on our primary outcome (HbA1c) and estimated attrition based on our previous studies in this population. Power calculations were based on standard deviations (SD) for changes in baseline to follow-up from our prior pilot study and assumed 80% power for a one-sided test at alpha of 0.05 corresponding to our hypothesis that the intervention would improve glycemic control and other outcomes. With the outcome of change in percent HbA1c from baseline to follow-up, using a SD of the change of 1.3937 for a minimum important difference of 0.5 in the change, the sample size needed is n=196 (n=98 in each of the two study arms). This sample size also provides 80% power for differences between arms in change in diabetes distress of 0.256 points, change in food insecurity of 1.3 points, and proportion at follow-up of 0.16 (e.g., 0.36 vs. 0.20) or greater for any binary outcome such hospitalization or emergency department visit. Anticipating attrition of 20%, the total sample size needed at recruitment would be at least 245. To be conservative, we enrolled 281 participants to account for the possibility of higher attrition than anticipated.

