## 6) Framework

The superiority hypothesis testing framework will be used, testing whether exposure to the intervention results in better outcomes than exposure to the control arm. Comparisons will be presented as differences between arms in changes in outcomes from baseline to endline.

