## 8) Timing of final analyses

Analysis is planned to begin in March 2025 upon completion of all field data collection in February 2025, when the 6-month follow-up of all participants is done. Analysis to evaluate the durability of the intervention will commence after the end of 12-months of follow-up of the intervention arm (July 2025).

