# Section 4: Statistical Principles

## 1) Confidence intervals and P Values

- a. **Level of statistical significance.** No significance testing will be conducted unless required by a journal. We will report 95% confidence intervals and exact p-values (or  $p<0.001$ ).
- b. **Description and rationale for any adjustment for multiplicity and, if so, detailing how the type I error is to be controlled.** The primary outcomes were established in the protocol, and thus no adjustments will be made for multiplicity.
- c. **Confidence intervals to be reported.** 95% confidence intervals will be reported alongside exact p-values.

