## 2) Analysis methods

- a. **Preliminary/Descriptive analyses.** Frequency tables for all variables and measures of central tendency and variability for continuous variables will characterize the sample and be stratified by randomization arm to check for non-equivalence. If the two arms differ at baseline on any covariates, the Rubin causal model (e.g., propensity scores, double- robust estimation) will be used to obtain the desired marginal effect estimates under the counterfactual assumption of balanced arm. Although the computerized data collection protocol and the presence of an interviewer should minimize missing data, the analyst will examine patterns of non-response, and inspect distributions of mediating and outcome variables to identify outlying or unusual values and assess distributional characteristics. Validity and reliability of scale constructs via confirmatory factor analysis and internal consistency will be verified.

**Analyses for Aim 1 (Diabetes and other clinical health outcomes):** The intervention is intended to improve clinical outcomes suggested by our intervention model. Specifically, the hypothesis is that the CHEFS-DM intervention will lead to improved (i.e., lower) mean HbA1c (primary outcome). For the primary analysis,

an intent-to-treat analysis of covariance will be done using the Stata regress and/or sem procedure with the primary outcome being changes from baseline to six months. The data for this analysis will be constructed in wide form, i.e., with an individual being a row in the data and the columns being the variables from both baseline and six months. The model will regress the change in an outcome variable on the baseline value of that outcome and arm (intervention or control). The model will be estimated by least-squares when using the regress procedure. Additional analyses will be done to a) check robustness if the two arms differ at baseline by controlling for the propensity score (or the covariates that were important in the propensity score); and b) adjust for medication use. If covariates have missing data, the sem procedure will be used with full information maximum likelihood to incorporate all covariate data under the assumption that missingness is at random.

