## Section 7: Changes from previous Protocol/SAP version

Protocol/SAP Version 2 changes: This version of the Protocol/SAP includes several changes to the trial approved by NIH (January 2024) and the UCSF IRB since the initial Protocol/SAP (Version 1) was registered.

- Sample size change: Our original proposed sample size was n=440 (n=220 in each arm). Given challenges with recruitment during and after the COVID pandemic, we re-calculated the sample size using updated power calculations with early data from the trial for the standard deviation in HbA1c and assuming 80% power for a one-sided test at alpha of 0.05 rather than 90%. Our new minimum sample size was calculated as n=246 (n=123 in each arm). As recruitment has ended as of June 2024, the final actual sample size is n=281 (n=156 in intervention and n=125 in control).
- Reduced measures: To reduce participant and staff burden, we reduced the number of measures and procedures. The changes included:
  - Removed fasting requirement and therefore fasting glucose and fasting lipids (still measuring non-fasting lipids)
  - Removed the following scales or measures at all time points:
    - Anxiety
    - Physical activity
    - Social support
    - Select items on economic status
    - Waist and hip circumference
  - Reduced the following scales or measures at all time points:
    - Reduced food security scale to retain adult items only
  - Removed the following measures at 12 months only
    - Weight
    - Blood pressure
- Medical record review: Allowed using an A1c from the medical record *if* blood draw was not possible at follow-up, if medical record A1c is available within the assessment time frame, and with the consent of the participant. We are not collecting medical record information on healthcare utilization and medications as this was not possible given the final sample was recruited from across the community and a wide array of healthcare settings/systems with variable payers.
- Statistical model: Our primary analysis will employ analysis of covariance rather than mixed effects (mixed effects will be employed as a secondary analysis).

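### HbA1c power rests on a one-sided 5% test, but the plan reports 95% intervals with no stated sidedness, and the 0.16 detectable difference does not hold for every binary outcome

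*Combined protocol and SAP*

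**What the plan says.** **Power basis.** Section 3, Sample size, "assumed 80% power for a one-sided test at alpha of 0.05" and ties this to the directional hypothesis of benefit. The inputs are an SD of 1.3937 for the change in HbA1c and a minimum important difference of 0.5. They lead to 98 per arm (196 in total), or 245 with 20% attrition. Section 7 repeats the one-sided basis.

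**Binary outcomes.** The same paragraph says this size also gives 80% power for a difference in "proportion at follow-up of 0.16 (e.g., 0.36 vs. 0.20) or greater for any binary outcome".

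**Inference.** Section 3, Framework: "The superiority hypothesis testing framework will be used". The wording there is directional, but no alpha or sidedness is set. Section 4, item 1: "No significance testing will be conducted unless required by a journal", and "95% confidence intervals will be reported alongside exact p-values". Neither the intervals nor the p-values are labelled one- or two-sided.

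**Primary model.** Section 6, Analysis methods, specifies ANCOVA: "The model will regress the change in an outcome variable on the baseline value of that outcome and arm (intervention or control".

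**Numbers and timing.** Section 7 reports the enrolment: "the final actual sample size is n=281 (n=156 in intervention and n=125 in control". Section 3, Timing of final analyses: "Analysis is planned to begin in March 2025".

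**The concern.** The test that was powered is not the one the planned interval reflects. If a one-sided conclusion is intended, the matching display is a 90% interval or a one-sided 95% bound, and neither is planned. If the 95% interval is to carry the conclusion, the stated 80% is not its power. The Framework section adopts hypothesis testing and Section 4 largely disclaims it, so no section says which rule decides the HbA1c result.

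Two things are at stake. The reader cannot tell what power the reported interval has. And for a moderate observed effect, the choice of sidedness determines whether the result reads as positive. If that choice is left open, it can be made after the data are seen. The 95% interval does not itself inflate type I error.

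The binary statement is a separate point. The detectable difference at a fixed sample size depends on the underlying proportions, so one figure cannot serve all binary outcomes. Section 6 lists several (HbA1c below 9%, low food security, acute care use, hospitalization, missed visits) without expected rates.

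**Working it through.** **Inputs.** From Sample size: SD of change 1.3937, difference 0.5, one-sided alpha 0.05, 98 per arm, attrition 20%. From Section 7: 156 and 125 enrolled. Section 6, Missing data, does not impute missed visits, so completers are the relevant number: 156 × 0.8 = 124.8 (taken as 125) and 125 × 0.8 = 100. Equal attrition in the two arms is an assumption.

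**1. The plan's own figure.** n per arm = 2(z₁₋α + z₁₋β)² SD² / d² = 2 × (1.645 + 0.842)² × 1.3937² / 0.5² = 96.1, so 97. The stated 98 agrees. 196 / 0.8 = 245, as stated. With z = 1.960 in place of 1.645 the formula gives 122.0 per arm (123 by the t-test), so the stated size depends on the one-sided choice.

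**2. Change-score power** (noncentral t, SE = SD × √(1/n₁ + 1/n₂)):

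| Completers | SE | One-sided 5% | Two-sided 5% | Two-sided detectable difference |
|---|---|---|---|---|
| 98/98 | 0.199 | 80.4% | 70.5% | 0.56 |
| 125/100 | 0.187 | 84.6% | 75.9% | 0.53 |
| 156/125 (no attrition) | 0.167 | 90.9% | 84.6% | 0.47 |

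Starting from 156/125, power stays at 80% or more up to about 30% attrition one-sided (109/87), but only up to about 11% two-sided (138/111). The planned attrition is 20%.

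**3. Where the two rules disagree at 125/100.** The one-sided 5% threshold is 1.652 × 0.187 = 0.309. The 95% interval excludes zero from 1.971 × 0.187 = 0.368. An observed benefit of about 0.31 to 0.37 is therefore positive one-sided while the interval includes zero.

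**4. Allowing for ANCOVA.** With equal variances at the two visits and correlation ρ (both assumptions; the documents give no ρ), residual SD = 1.3937 × √((1 + ρ)/2), with one degree of freedom fewer. Two-sided power:

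| ρ | 98/98 | 125/100 |
|---|---|---|
| 0.5 | 82.3% | 86.7% |
| 0.8 | 75.0% | 80.1% |
| 0.9 | 72.7% | 78.0% |

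Power falls below 80% once ρ exceeds about 0.59 at 98/98 or about 0.81 at 125/100.

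**5. Binary outcomes, 98 per arm, difference 0.16.** Power = Φ[(0.16 − z·s₀)/s₁], where s₀ is the pooled and s₁ the unpooled standard error.
- 0.36 vs 0.20 (the plan's example), one-sided: (0.16 − 1.645 × 0.0641)/0.0631 = 0.863, giving 80.6%. The example reproduces.
- 0.58 vs 0.42, one-sided: (0.16 − 1.645 × 0.0714)/0.0705 = 0.603, giving 72.7%.

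| Proportions | One-sided | Two-sided |
|---|---|---|
| 0.30 vs 0.14 | 86.0% | 77.6% |
| 0.36 vs 0.20 | 80.6% | 70.6% |
| 0.40 vs 0.24 | 77.9% | 67.3% |
| 0.50 vs 0.34 | 73.7% | 62.3% |
| 0.58 vs 0.42 | 72.7% | 61.2% |
| 0.80 vs 0.64 | 80.6% | 70.6% |

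Power is below 80% for lower proportions of about 0.21 to 0.63 one-sided and about 0.12 to 0.72 two-sided. The worst-case detectable difference is about 0.18 one-sided and 0.20 two-sided. The plan's example lies almost at the edge of the range where its claim is true.

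**The case against.** The one-sided choice is disclosed, repeated in Section 7 and justified by a directional hypothesis, and the sample size follows correctly from it. Section 4 describes an estimation approach. Sizing a trial one-sided and then reporting 95% intervals is not in itself a contradiction, and the band from 0.31 to 0.37 matters only if someone applies an accept/reject rule. The 75.9% is also not the power of the planned ANCOVA, which at 125/100 keeps 80% two-sided up to a correlation of about 0.81. With full follow-up even the change score gives 84.6%. Recruitment is closed, and the interval will show the achieved precision directly. The binary shortfall concerns secondary outcomes and is modest: at 125/100 the one-sided minimum is about 77%.

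Much of this stands. The sample size is not miscalculated, and low power for the primary analysis is not shown. What remains is that the Framework section still adopts hypothesis testing, Section 4 allows it if a journal asks, and the p-values carry no sidedness. The ANCOVA gain rests on a correlation the plan never states. The binary sentence is made for 98 per arm and for all binary outcomes, and on those terms it is incorrect.

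**Conclusion.** The concern holds, and the plan should be corrected on two counts.

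First, the power statement and the reporting plan do not match. Moving from the one-sided test to the one implied by a 95% interval costs about 9 to 10 percentage points of change-score power at the relevant numbers of completers. How much ANCOVA recovers is unknown without the correlation, so the defect is undocumented power and an unstated decision rule, not demonstrated underpowering. These figures rest on the plan's SD and difference. Those at 125/100 also assume 20% attrition in each arm, and the ANCOVA figures assume equal variances.

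Second, the binary claim is wrong as written on the plan's own one-sided basis. For mid-range proportions at 98 per arm, power for a 0.16 difference falls as low as 72.7%.

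**What to change.** Before the arms are compared:

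1. State the sidedness of the HbA1c inference once, and bring the Framework section and Section 4, item 1, into line with it. Two-sided 5% is simplest, because it matches the 95% interval already planned. If one-sided is kept, plan a 90% interval or a one-sided 95% bound, and label the p-values.
2. Restate HbA1c power on that basis for 156/125 enrolled and the expected completers. If ANCOVA power is quoted, name the assumed correlation and show a range.
3. Replace the general binary claim with limits at 98 per arm. One-sided: 0.16 holds for a lower proportion up to about 0.20 or above about 0.63. Two-sided: it holds up to about 0.12 or above about 0.72, and the detectable difference from 0.20 is about 0.18. Give the worst case as well (about 0.18 one-sided, 0.20 two-sided).
4. If two-sided, scale the other detectable differences by 0.5606/0.4968 = 1.13: food insecurity from 1.3 to about 1.47 points, and diabetes distress from 0.256 to about 0.29.

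The cost is SAP wording and restated figures, with no extra participants. The stated power on the two-sided change-score basis will look somewhat less favourable.
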